Location and type of surgical procedure, duration of procedure, and duration of intravenous sedation will also be recorded. Total time in the operating room will also be noted. Time admitted to PACU, time clinically ready for discharge, time actually discharge, PACU medications for nausea/vomiting and PACU meds for pain will all be recorded prior to discharge.

Post-operative pain will be assessed using the Visual Analogue Scale (0-100) prior to being discharged from PACU. Time to discharge and amount of pain medication taken in the PACU will be recorded.

Patients will be contacted 8 hours, 12 hours, 24 hours, 48 hours and 72hrs after surgery by the operative surgeon or research coordinator to assess their pain scale and pain medication intake. Patients will be seen for routine post-operative follow-up visits at two, six, twelve, twenty-four, and fifty-two weeks. At these times, patients will be assessed for pain, residual neurological symptoms, and signs of infection. Patients will also be asked if they were satisfied with their postoperative pain control. Total duration of study will be fifty-two weeks. Data collection documents will be distributed to the patients at time of surgery to assist in patient understanding.

Inclusion criteria

1. Patients at least 18 years old.
2. Male or Female
3. All racial and ethnic groups
4. Fractures and fracture/dislocations of the foot, ankle, tibia, fibula, elbow, forearm, wrist and hand
5. Patients who opt for surgical treatment of their fractures.
6. Patients who consent to be randomized.
7. Patients who are willing to follow-up for a minimum of 52 weeks.

Exclusion criteria

1. Patients younger than 18 years old.
2. Patients who are on chronic opioids
3. Patients who abuse opioids
4. Patients who are unwilling to follow-up for a minimum of 52 weeks.
5. Neurologic condition that could interfere with pain sensation

Characteristics of the Research Population

1. **Total number of subjects:** 100 subjects
2. **Gender:** Male or Female
3. **Racial and Ethnic Origins:** All are included

Study payments/cost:

Study participants will not incur any additional costs or payments as a result of this study. Any additional costs will be absorbed by the NYU Departments of Orthopaedics and Anesthesia

Potential Risks and Discomforts:

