Participant medical information will be stored electronically within a password protected spreadsheet available only to the PI, co-investigators, and research staff as necessary for data analysis. The names, social security numbers, and medical record numbers of the study participants will be deleted from their stored medical information and replaced with a linkage code. Access to participant medical information contained within the registry will be restricted.

Protection Against Risk: All procedures will be performed as outlined above. After the procedure pt will be contacted 6-8 hours after surgery and at 24 hours, 48 hours and 72hours after surgery by the operative surgeon or research coordinator to assess their pain scale and pain medication intake. Patients will be seen for routine post-operative follow-up visits at two, six, twelve, twenty-four, and fifty-two weeks. At these times, patients will be assessed for pain, residual neurological symptoms, and signs of infection, and starting at the six week time point, patient's functional status will be assessed using the Disability of the Arm, Shoulder and Hand (DASH) and SMFA scores, both are widely accepted and validated functional measures.

Method of Subject Identification and Recruitment: All patients seen in the outpatient office, who fit the inclusion criteria will be asked to participate in the study.

Subject/Representative Comprehension: None

Debriefing Procedures: All patients will have regular follow-up at which point, all questions regarding the study can be answered.

Documentation of Consent: A copy of the signed consent form will be securely kept for our records.

Statistical analysis plan:

A preoperative power analysis was performed. On a VAS scaled from 1-100, assuming a standard deviation of 20, the number needed to detect a 10 point change in VAS was 38. Assuming a drop out rate of 20%, we will require 50 patients in each group to determine significance. The primary end points of the study for Visual Analog Score will be assessed using two-group t-tests (Mann-Whitney U test where appropriate). Amount of pain medication utilized post operatively will be assessed using Student t-tests. Residual neurological symptoms and signs of infection will be reported as descriptive statistics. Descriptive statistics will be reported as means +/- SD for continuous variables and as frequencies and percentages for categorical variables.

References

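### VAS is compared by two-group tests on the scores present at a given time, ignoring a missing patient's other readings; a repeated-measures model would be a cheap, modest improvement

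*Combined protocol and SAP*

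**What the plan says.** The analysis of the main outcome is one sentence in the Statistical analysis plan: "The primary end points of the study for Visual Analog Score will be assessed using two-group t-tests (Mann-Whitney U test where appropriate". Drop-out appears only in the sample size: "the number needed to detect a 10 point change in VAS was 38", then "Assuming a drop out rate of 20%, we will require 50 patients in each group to determine significance".

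Pain is measured repeatedly. Data collection has a reading in the PACU ("Post-operative pain will be assessed using the Visual Analogue Scale (0-100) prior to being discharged from PACU") and then a series after surgery: "Patients will be contacted 8 hours, 12 hours, 24 hours, 48 hours and 72hrs after surgery by the operative surgeon or research coordinator". Pain is assessed again at clinic visits: "Patients will be seen for routine post-operative follow-up visits at two, six, twelve, twenty-four, and fifty-two weeks". The Data Monitoring Plan and Protection Against Risk repeat the early schedule without the 12 h contact.

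The document gives no rule for missing scores, no analysis population, no repeated-measures model, no missing-data sensitivity analysis and no procedure after a missed contact. It does not say which VAS time is primary.

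**The concern.** A t-test or Mann-Whitney test at one time uses only patients with a score at that time. With no other rule stated, this is a complete-case analysis at each time. A patient who misses the 24 h contact but has PACU, 8, 12, 48 and 72 h scores contributes nothing at 24 h.

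Two things are at stake. One is precision: the other readings carry information about the missing one. The other is bias. The Scientific or Scholarly Rationale places rebound pain after a block at roughly 12-24 h and says that narcotics can control it. If pain or opioid use makes a patient harder to reach, and one arm has more of it, that arm loses more of its high scores and the estimated difference shrinks in the window where the trial expects its effect.

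**Working it through.** **Inputs from the Statistical analysis plan.** SD 20, target difference 10 points, 38 raised to 50 per group, drop-out 20%. **Assumed, because not stated:** two-sided 5% level; within-patient correlation ρ of 0.3-0.7; five readings (8, 12, 24, 48, 72 h); 24 h as the time of interest; and the missed-contact rates below.

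**1. The plan's own figure.** 38/(1 − 0.20) = 47.5, so 48, against a stated 50. The drop-out step reproduces within 2 patients, and 50 × 0.8 = 40 analysed. The plan thus treats drop-outs as lost to the analysis, which fits the complete-case reading. The base of 38 does not reproduce at two-sided 5% and 80% power, where 63 per group are needed. That is a separate matter and nothing below depends on it.

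**2. Precision.** Suppose 20% of each arm miss only the 24 h contact. The two-group test uses 40 per arm. With exchangeable correlation, the four other readings explain R² = 4ρ²/(1 + 3ρ) of the 24 h variance. A likelihood analysis then has effective n = 1/[(1 − R²)/40 + R²/50].

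- ρ = 0.3: R² = 0.36/1.9 = 0.19, effective n = 41.6
- ρ = 0.5: R² = 1.00/2.5 = 0.40, effective n = 43.5
- ρ = 0.7: R² = 1.96/3.1 = 0.63, effective n = 45.8

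Other correlation and missingness patterns give 41.1-46.1. Power for 10 points is 61% with 40 per arm, about 62%, 64% and 67% with the model at the three correlations, and 70.5% with complete data on 50. If the 20% have no reading at any contact, a model of the contacts recovers nothing and n stays at 40.

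**3. Bias.** Simulated trials: 50 per arm, SD 20, true 24 h difference 10, ρ of 0.5-0.7. Where missingness depends on pain, about 25-27% against 18-19% are missing at 24 h. The ranges cover several runs of 400 to 4,000 trials.

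| A missed 24 h contact depends on | Two-group estimate | Likelihood model on all readings |
|---|---|---|
| nothing (random, about 18%) | unbiased, variance 1.07-1.12 times larger | unbiased |
| recorded 12 h pain, arms differ at 12 h | 9.0-9.5 | about 10 (9.9-10.2) |
| 12 h pain, arms do not differ at 12 h | 9.9-10.1 | not needed for bias |
| the unseen 24 h pain | 8.7-8.9 | 9.2-9.6 |

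The rows agree with each other. If missingness acts through 12 h pain, its effect on the 24 h mean is multiplied by ρ. Taking the loss in the last row as 10 − 8.9 = 1.1, the second row should be near 10 − 0.5 × 1.1 = 9.45 and 10 − 0.7 × 1.1 = 9.23. If the arms have the same 12 h pain and the same missingness, the shifts cancel, as the third row shows.

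With steeper dependence (about 32% against 20% missing, ρ = 0.7) the two-group estimate falls to 8.1.

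**4. An extreme case.** If exactly the worst 20% on 12 h pain in one arm all miss the 24 h contact, that arm's observed mean is too low by ρ × 20 × 0.280/0.8 = 7.0ρ, which is 2.1, 3.5 or 4.9 points at ρ = 0.3, 0.5 or 0.7. This is a one-arm construction, not a forecast.

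**5. Size against noise.** With 18% missing, 50 × 0.82 = 41 per arm, and the standard error is 20 × √(2/41) = 4.4. A bias of 0.5-1.0 point is 0.11-0.23 of that. Mean squared error in the second row was 20.1 for complete cases against 19.7 for the model at ρ = 0.5, and 20.2 against 18.1 at ρ = 0.7.

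**The case against.** A two-group test at a given time is a valid method, and unbiased when a missing score is unrelated to pain. The plan does not contradict itself here, and a mixed model could be called a preference. The strongest points on this side are:

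- **The 20% is not a missed-contact rate.** A reader might infer that a fifth of the early scores will be missing. The documents give 20% as overall drop-out in a study lasting 52 weeks. Missingness within 72 h could be lower or higher. This stands, so the rates above are assumptions.
- **Not every VAS depends on reaching the patient at home.** A reader might infer that all scores are taken by telephone after discharge. The PACU score precedes discharge, later pain is assessed at visits, and for 8-72 h the text says only that patients are contacted. This stands. The PACU score is also one more reading that a test at a later time does not use.
- **The direction is not certain.** Bias needs an arm difference in whatever drives missed contacts. If the arms are still alike at 12 h, there is none. Comfortable patients who resume activity could equally be the ones not reached. This stands.
- **The remedy fits the simulated mechanism better than the feared one.** If patients are missed because of their pain at that moment, the model recovers only part of the loss: (9.3 − 8.9)/1.1 = 36% at ρ = 0.5 and (9.6 − 8.9)/1.1 = 64% at ρ = 0.7. If the 12 h contact is not made, as two sections imply, less is recorded to adjust on.

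These points limit the size of the concern. They do not remove it: the scores are scheduled anyway, the named tests do not use them, and the model was not worse in mean squared error in any mechanism simulated.

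**Conclusion.** The point holds as a low-cost improvement, not as a flaw that invalidates the comparison. The plan's tests leave out a patient at any time without a score, although other acute scores will usually be on file.

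Under the assumptions stated, the loss is about 0.5-1.0 point of a 10-point difference if missingness follows recorded pain that differs by arm, 1.1-1.3 points if it follows unseen pain, and only 7-12% more variance if it is random. The precision regained at 24 h is worth about 1 to 6 patients per arm.

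A reader might go further and conclude that the trial's result will be biased toward no difference, or that a mixed model would cure the problem. The documents support neither. They give no missed-contact rate and no evidence on who is missed, and the model relies on missingness depending only on recorded scores.

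**What to change.** In the Statistical analysis plan:

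- Analyse the PACU and 8, 12, 24, 48 and 72 h VAS with a mixed model for repeated measures: arm, time, arm-by-time and unstructured covariance, on all randomized patients with any reading. Enter the PACU score as an outcome, not a covariate, since it is taken after randomization.
- Take the arm contrast at the chosen time from that model. The plan must first name that time.
- Keep the t-test (or Mann-Whitney test) at that time as a sensitivity analysis.
- State that later contacts are attempted after a missed one, and report missed contacts by arm and time.
- Reconcile the 12 h contact across Data collection, the Data Monitoring Plan and Protection Against Risk.

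The cost is a few sentences and a standard model, with no added patients or measurements. The downside is the assumption that missingness depends only on recorded scores. Where that fails, only part of the bias is removed. A patient with no reading after discharge contributes little, since only the PACU score is available.

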All patients being treated with open reduction internal fixation for foot, ankle, tibia, elbow, forearm and wrist fractures at New York University Medical Center, NYU-Hospital for Joint Diseases will be asked to participate in this study. At the patients preoperative office visit, they will be asked to participate in the study and provided a copy of the consent form at that time which they can take home with them. All questions will be answered and they will be asked verbally if they will consent to being a part of the study. Patients will then have the opportunity to either sign the written consent forms or wait till the surgical date to think about the study and any additional questions they may have. At the time of surgery, patients will be consented for surgery. If the patient did not give written consent at the preoperative visit, they will be asked if they have any questions about the study. All questions will again be answered. They will then be asked verbally if they are willing to participate in the study, if they respond yes, then written consent will be obtained at that time.

Randomization

Patients will then be randomized (using an online randomizer, similar to a flip of a coin) to one of two anesthetic protocols: regional block with single dose of anesthetic versus regional block with continuous infusion using an OnQ pump. If for some reason, the anesthesiologist feels that a patient would benefit from one type of anesthesia over another, the patient will be removed from the study and given that type of anesthesia.

Intervention

Patients will be randomized to one of two anesthetic protocols: general anesthesia/sedation with a single shot, peripheral nerve block versus general anesthesia/sedation with a continuous, peripheral nerve block.

All anesthesia will be provided by an attending anesthesiologist with or without an anesthesiology resident/CRNA. Patients will have standard ASA monitors placed (pulse oximeter, blood pressure, EKG) and an intravenous line started. Sedation will be given using a combination of midazolam (1-4 mg) and fentanyl (25-100 mcg). Patients in both groups will receive an ultrasound-guided peripheral nerve block. The block will be either an infraclavicular brachial plexus block or a popliteal nerve block, depending on

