the location of the fracture. The appropriate region will be prepped with a chlorohexidine solution on the appropriate surgical side and the appropriate site will be visualized under ultrasound. For the group receiving a single shot block, a 22 gauge, 3.5 inch needle will be used and 20cc of 2% lidocaine with 1:200,000 epinephrine + 20 cc of 0.5% bupivacaine with 1:300,000 epinephrine will be injected around the nerve after confirming negative aspiration every 5 cc. For those receiving a continuous infusion, a 17 gauge Tuohy needle will be used and 20cc of 2% lidocaine with epinephrine + 20 cc of 0.5% bupivacaine with 1:300,000 epinephrine will be injected around the nerve after confirming negative aspiration every 5cc. Once the injection is complete, an indwelling catheter will be placed with its tip location confirmed and then secured at the skin.

After placement of the regional block, general anesthesia/sedation will be administered and maintained at the discretion of the anesthesiologist. Induction of anesthesia will involve IV propofol (2mg/kg) and fentanyl (1-2mcg/kg). Neuromuscular blockade will be used at the discretion of the anesthesiologist and will be reversed appropriately. Anesthetic maintenance will involve inhalational agents, IV agents, air, and oxygen. Fentanyl will be the only intraoperative analgesic used and will be dosed as determined by the anesthesiologist.

After completion of the surgery, patients will be taken to the PACU where those with continuous catheters will have an OnQ pump attached to it. The patient will begin receiving a continuous infusion of 0.2% ropivacaine through the catheter at a rate of 8 cc/hr. The patient will be discharged home with the catheter for 48 hours. The study participant will self-discontinue the catheter in 2 days. This involves removing the tegaderm dressing and gently pulling the catheter out from under the skin. A bandage may then be applied. [name], our anesthesiology RN, will be available via phone to answer any questions study participants may have regarding discontinuation of the catheter. Breakthrough pain while in the PACU will be treated with IV fentanyl and PO Percocet as needed.

Postoperatively, all patients will be discharged home with a prescription for Percocet 5/325 with instructions to take 1-2 tabs every 4-6hrs as needed for pain.

Data collection

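### Pain-medication use is tested only with the equal-variance Student t-test; Welch is a nearly free safeguard if the arms end up unequal in both size and spread (low severity).

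*Combined protocol and SAP*

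**What the plan says.** - **Medication test** (Statistical analysis plan): "Amount of pain medication utilized post operatively will be assessed using Student t-tests". No unequal-variance, rank, count-model or transformation alternative is attached to this outcome.
- **VAS test** (the sentence before): "will be assessed using two-group t-tests (Mann-Whitney U test where appropriate". The rank option belongs to VAS alone, and the wording about primary end points is also confined to VAS.
- **Nature of the outcome** (Intervention): patients go home with Percocet, "with instructions to take 1-2 tabs every 4-6hrs as needed for pain". In recovery, "Breakthrough pain while in the PACU will be treated with IV fentanyl and PO Percocet as needed".
- **Collection** (Data collection): PACU medication is recorded, and "Patients will be contacted 8 hours, 12 hours, 24 hours, 48 hours and 72hrs after surgery" to ask about pain and medication intake.
- **Allocation** (Randomization): an online randomizer described as "similar to a flip of a coin", with no blocking mentioned. The anesthesiologist may also remove patients from the study.
- **Size** (Statistical analysis plan): 50 per group, allowing for 20% dropout.
- **Reporting**: means with SDs for continuous variables. No confidence interval is promised for medication.

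**The concern.** The Student test pools the two variances. That is harmless when arm sizes are equal or spreads are equal, but not when both differ. If the smaller arm is the more variable, pooling understates the standard error and the test rejects too often. In the reverse case it rejects too rarely.

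Both conditions are possible here. An as-needed amount cannot fall below zero, so its spread often moves with its mean, and the two arms are expected to differ in mean if the pump works. Simple randomization leaves arm sizes to chance. The plan gives VAS an alternative test and gives medication none. At stake is the p-value for the only efficacy outcome besides VAS that is assigned a test.

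**Working it through.** **Plan's own figure.** There is none for medication. The stated sample size concerns VAS and does not bear on this point. The documents give no mean, SD or share of non-users for medication, so every distribution below is an assumption.

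**Arm sizes.**
- 100 patients with 20% dropout leave 100 × 0.8 = 80 completers.
- With arm size Binomial(80, 0.5), P(32 v 48 or worse) = 2 × P(X ≤ 32) = 9.3%. Only half of such splits fall in any one direction.
- For all 100 patients, the 95% range is 40 to 60 per arm. A 60:40 split or worse has probability 5.7%; 55:45 or worse, 36.8%.

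**Student type I error, large-sample formula.**
- True variance of the difference: V = s1²/n1 + s2²/n2
- Variance the test uses: P = [(n1−1)s1² + (n2−1)s2²]/(n1+n2−2) × (1/n1 + 1/n2)
- Error = 2 × [1 − Φ(t × √(P/V))], with t = 1.991 on 78 df

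Worked case, n1 = 32 with SD 2 and n2 = 48 with SD 1:
- V = 4/32 + 1/48 = 0.1458
- P = (31×4 + 47×1)/78 × (1/32 + 1/48) = 2.192 × 0.0521 = 0.1142
- √(P/V) = 0.885, and 1.991 × 0.885 = 1.762, so the error is 7.8%

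Reverse case, SD 1 in the arm of 32: V = 0.1146, P = 0.1462, error 2.5%.

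The formula mixes a t cut-off with a normal tail and so gives 4.7% when spreads are equal. Simulation (normal data, equal means, 40,000 runs per setting) avoids this:

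| Arms, SD ratio | More variable arm | Formula, Student | Simulated Student | Simulated Welch |
|---|---|---|---|---|
| 32 v 48, 2 | smaller | 7.8% | 8.2% | 4.9% |
| 32 v 48, 2 | larger | 2.5% | 2.9% | 5.0% |
| 32 v 48, 1.5 | smaller | 6.6% | 6.7% | 4.8% |
| 32 v 48, 1.5 | larger | 3.1% | 3.5% | 4.9% |
| 40 v 40, 2 | equal sizes | 4.7% | 5.1% | 5.0% |

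Averaged over coin-flip sizes with 80 completers and normal data, Student's simulated error is 5.1% at either ratio.

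**Skewed counts** (assumed negative binomial counts, some with extra zeros):
- Same distribution in both arms, splits up to 60:40 and 48:32: Student 4.6-5.1%, Welch 4.6-5.2%.
- Equal means, SDs about 5.9 and 12.7 (ratio about 2.1). At 60:40 with the smaller arm more variable: Student 9.5%, Welch 6.5%. Reverse: 3.6% and 5.6%. At 50:50: 6.0% and 5.9%. Averaged over coin-flip sizes for 100 patients: 6.2% and 6.0%.
- Extreme ratio of about 4, at 60:40: Student 13.2%, Welch 8.2%. Welch reduces the problem but does not remove it when skew and unequal spread are both severe.

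**Are ratios of 1.5 to 2 plausible?** Take a negative binomial with mean 12 and size 1.5: variance = 12 + 144/1.5 = 108.
- Setting 10% v 40% of patients to zero gives variances 0.9×252 − 10.8² = 110.2 and 0.6×252 − 7.2² = 99.4. The SDs are 10.5 and 10.0, ratio 1.05.
- Means 12 v 8 without extra zeros give SDs 10.4 and 7.1, ratio 1.46.

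A ratio of 2 is therefore a stress case; about 1.5 can arise.

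**Power in those two cases, 40 per arm:**

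| Case | Student | Welch | Mann-Whitney |
|---|---|---|---|
| 10% v 40% taking none | about 35% | about 35% | about 60% |
| Mean 12 v 8, no extra zeros | about 52% | about 52% | about 44% |

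With equal means but different shapes, the Mann-Whitney test rejected 46% of the time in one assumed scenario. It is not a test of means.

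**The case against.** The strongest reply is that this is a drafting preference. With 40 to 50 per arm the t-test tolerates skew and zeros, and unequal arm sizes alone do no harm. A material error needs clearly unequal spread together with an uncommon split. The mechanism that comes first to mind, more non-users in the pump arm, hardly changes the SD (ratio 1.05). Averaged over possible splits the Student error is close to nominal, Welch is not exact for skewed counts, and medication is not a primary end point. All of this stands, and it sets the severity.

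It does not remove the point. The trial will be analyzed with one realized split, and an average over other splits does not protect that p-value. Choosing the test after seeing the arm sizes and spreads would invite doubt. Prespecifying Welch costs almost nothing: with equal variances its power differed from Student's by 0.3 percentage points at 32 v 48 and not at all at 40 v 40.

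A reader might infer that tablet counts and coin-flip allocation in themselves make the planned test and its interval unreliable. The documents do not support that. They give no medication SD from which unequal spread could be shown, and they promise no interval for this outcome. A reader might also infer that Welch cures the power loss with many non-users; the second table shows that it recovers none of it.

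**Conclusion.** The point holds as a low-severity, nearly free improvement. The plan fixes the pooled-variance test for an outcome whose spread may differ between arms, under allocation that does not secure equal arms. At 32 v 48 and assumed SD ratios of 1.5 to 2, the type I error is about 7-8% or about 3%, depending on which arm is more variable. Welch holds about 5% with normal data and reaches about 6.5% with strongly skewed counts at a ratio near 2. Such a split or worse has probability about 9% with 80 completers, and the Student error averaged over coin-flip sizes is about 5-6%. These figures rest on assumed distributions, 20% dropout and simple 1:1 randomization without blocking. The effect on the trial's primary VAS comparison is nil.

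**What to change.** In the Statistical analysis plan, replace the Student t-tests for pain medication with: *Welch (unequal-variance) t-test with 95% CI for the difference in means*. Add a Mann-Whitney test as a prespecified supportive analysis only, because its power relative to the t-test can go either way and it does not test means.

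Cost: one sentence, no new data, and essentially no power when variances are equal. The interval is an addition to the plan rather than the correction of a stated one.
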